5.1.3. General duration derivation and conversion

In instances where duration or time-to-event is calculated, the convention to be used unless otherwise specified is [later date] – [earlier date] + 1 day.

When converting a number of days to other units, the following conversion factors will be used:
1 year = 365.25 days; 1 month = 30.44 days.

5.1.4. Analysable value

Table (5.1.4) 1 - Definition of analysable value

General definition	
Non missing value	
Specific definitions	
Laboratory parameters	Only reliable values are considered for analyses. Unreliable values are flagged into the database.
ECG parameters	For the analysis of QT criteria per measurement time, only scheduled values will be analyzed.

5.1.5. First and last IMP intake dates

For patients having taken at least one dose of IMP, the dates of first and last IMP intake on the analysis period will be defined as follows:

- The date of the first IMP intake = min (first trifluridine/tipiracil intake date, first futuximab/modotuximab infusion date) within the analysis period.
- The date of the last IMP intake = max (last trifluridine/tipiracil intake date, last futuximab/modotuximab infusion date) within the analysis period.

After selection of the dates of first and last IMP intake as defined above, if these dates are missing or incomplete, the following substitution rules will be applied:

Table (5.1.5) 1 - Substitution rules of tIMP intake dates

Date to substitute		Substituted date
First IMP intake	./mmm/yyyy	Inclusion date* if complete with same month and year Otherwise 01/mmm/yyyy
	./.../yyyy	Inclusion date* if complete with same year Otherwise 01/JAN/yyyy
	./.../....	Inclusion date* if totally incomplete
Last IMP intake	./mmm/yyyy	Last available date** if same month and year Otherwise last day of the month/mmm/yyyy
	./.../yyyy	Last available date** if same year Otherwise 31/DEC/yyyy
	./.../....	Last available date**

Notes:

- Missing dates will be substituted only for patients having taken at least one dose of study treatment
./mmm/yyyy = missing day
./.../yyyy = missing day and month
./.../.... = totally missing date
- * inclusion date (or dispensation date if inclusion date is missing)
- ** Last available date (only for patients included) is defined as date of death if patient died, and as maximum date among completed dates relative to patient's information otherwise.

Note:

Cycles with both missing first and last IMP intake dates and with number of returned tablets equal to number of tablets delivered at the previous cycle (or with estimated number of tablets taken equal to 0) will not be taken into account.

5.1.6. Other dates

The rules for substitution of missing or incomplete death date are as follows:

Table (5.1.6) 1 - Substitution rules of death date

Date to substitute		Substituted date
Death date	../mmm/yyyy	Last available date* if same month and year Otherwise 01/mmm/yyyy
	../..../yyyy	Last available date* if same year Otherwise 01/JAN/YYYY
	../..../....	No substitution

Notes:

../mmm/yyyy = missing day
../..../yyyy = missing day and month
../..../.... = totally missing date

- * Last available date is defined as maximum date among completed dates relative to patient's information otherwise.

If no specific management of dates is defined, missing information is substituted as defined below:

Table (5.1.6) 2 - Substitution rules of dates if no specific management is defined

Date to substitute		Substituted date
Date	../mmm/yyyy	01/mmm/yyyy
	../..../yyyy	01/JAN/yyyy
	../..../....	No substitution

Note:

../mmm/yyyy = missing day
../..../yyyy = missing day and month
../..../.... = missing date

5.2. Specific analytic definitions and data handling conventions

5.2.1. Study patients: Disposition, baseline characteristics and follow-up

5.2.1.1. Disposition of patients

All treatment withdrawal reasons occurred in the study will be taken into account (adverse event, protocol deviation, progressive disease (radiological progressive disease, clinical progressive disease, radiological and clinical progressive disease), non-medical reason (consent withdrawal from study treatment, consent withdrawal including survival follow-up), lost to follow-up, physician decision or other medical reason).

5.2.1.2. Protocol deviations

Deviation categories have been defined in order to gather all the deviations relative to the same topic.

For the description of protocol deviations, the 6 following categories are considered in accordance with [ICH E3](#) guideline and [ICH E3 Q&A](#):

- Selection/inclusion criteria not fulfilled.
- Patient having withdrawal criteria but not withdrawn.
- Incorrect treatment or dose received.
- Forbidden concomitant treatment.
- Endpoint assessment possibly affected.
- Safety possibly affected.

5.2.1.3. Demographic data and other baseline characteristics

5.2.1.3.1. Demographic data

Age is calculated as difference between year of informed consent and year of date of birth.

5.2.1.3.2. History of Colorectal cancer

Primary tumour localisation:

- **Right** if primary tumour site = right colon⁽¹⁾ or transverse or other*
- **Left** if primary tumour site = left colon⁽²⁾ or rectum

(1) Right colon should include multilocalised right colon, ascending colon, cecum, appendix and hepatic flexure.

(2) Left colon should include multilocalised left colon, descending colon, sigmoid colon, splenic flexure and rectosigmoid segment.

*Other: in the case the patient present multiple tumours in both sides, the disease will be considered as "right-sided".

Site of metastasis is defined from History of colorectal cancer e-CRF page.

Number of metastatic site is defined as the number of distinct site of metastasis (whether the site is considered for target or non-target lesion) from History of colorectal cancer e-CRF page. Sites filled in 'Other' will be counted as 1 site.

Disease duration

Disease duration (years) is defined as (Inclusion date – date of the first diagnosis of colorectal cancer)/365.25

Time from first metastasis diagnosis to inclusion

Time from first metastasis diagnosis to inclusion (months) is defined as (inclusion date – first metastasis diagnosis date)/30.44

Progression free interval

Progression free interval (months) is defined as (Date of progression prior to the randomisation date – date of end of the last prior anti-cancer therapy*)/30.44.

The progression free interval of patients progressing during the last regimen is estimated to last one day.

*Including drug treatment, radiotherapy and surgery (whatever the intent).

Treatment free interval

Treatment free interval (months) is defined as (date of first IMP intake – date of end of the last prior anti-cancer therapy*)/30.44.

*Including drug treatment, radiotherapy and surgery.

Of note, in case of partial or incomplete date:

Table (5.2.1.3.2) 1 - Substitution rules of History of colorectal cancer

Missing diagnosis date		Substituted diagnosis date
./mm/yyyy	⇒	Diagnosis date = 01/mm/yyyy
./.../yyyy	⇒	Diagnosis date = 01/01/yyyy
Missing metastasis date		Substituted metastasis date
./mm/yyyy	⇒	Metastasis date = 01/mm/yyyy
./.../yyyy	⇒	Metastasis date = 01/01/yyyy
Missing start date of the last prior therapy		Substituted start date of the last prior therapy
./mm/yyyy	⇒	start date of the last prior therapy = 01/mm/yyyy
./.../yyyy	⇒	start date of the last prior therapy = 01/01/yyyy
Missing end date of the last prior therapy		Substituted end date of the last prior therapy
./mm/yyyy	⇒	end date of the last prior therapy = start date of the last prior therapy + 1day if same month and year otherwise: end date of the last prior therapy = 01/mm/yyyy
./.../yyyy	⇒	end date of the last prior therapy = start date of the last prior therapy + 1day if same year otherwise: end date of the last prior therapy = 01/01/yyyy
./.../...	⇒	end date of the last prior therapy = start date of the last prior therapy + 1day
Missing start date of a previous treatment	⇒	Substituted start date of a previous treatment
./mmm/yyyy	⇒	01/mmm/yyyy
./.../yyyy	⇒	01/JAN/yyyy
./.../....	⇒	Inclusion date

Note:
 ./mm/yyyy = missing day
 ./.../yyyy = missing day and month
 ./.../.... = missing date

RAS status

Table (5.2.1.3.2) 2 - RAS status

KRAS	NRAS	RAS
MUTANT	whatever (mutant, wild, missing)	MUTANT
whatever (mutant, wild, missing)	MUTANT	MUTANT
WILD	WILD	WILD
MISSING	WILD	NE
WILD	MISSING	NE
MISSING	MISSING	NE

Stage at diagnosis

Table (5.2.1.3.2) 3 - Staging based on classification

Stage in classes	AJCC stage	Dukes' classification	Astler-Coller modified Dukes' classification
	Stage 0	-	-
I-II	Stage I	A	A
I-II	Stage I	A	B1
I-II	Stage II-A	B	B2
I-II	Stage II-B	B	B2
I-II	Stage II-C	B	B3

III	Stage III-A	C	C1
	Stage III-B	C	C2
		C	C1/C2
		C	C1
	Stage III-C	C	C2
		C	C2/C3
		C	C3
IV	Stage IV-A		D
	Stage IV-B		
	Stage IV-C		

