5.1.2. Medical and therapeutic criteria

2. Participants must have histologically or cytologically confirmed adenocarcinoma of mCRC (all other histological types are excluded), not amenable to surgical intervention due to either medical contraindications or non-resectability of the tumour.
3. Based on ctDNA screening blood test analysis participants should be:
 - Without RAS (KRAS and NRAS) mutations in any of the following codons:
 - CCI [REDACTED]
 - CCI [REDACTED]
 - CCI [REDACTED]
 - Without BRAF CCI [REDACTED].
4. Participants must have measurable or non-measurable lesion according to RECIST v1.1.

5b. Participants must have received at least 2 prior regimens of standard chemotherapy for mCRC and had demonstrated progressive disease or intolerance to their last regimen. The following characteristics apply:

- Prior standard chemotherapy must not have included trifluridine/tipiracil but must have included all of the following agents approved and available in each country:
 - Fluoropyrimidines, irinotecan and oxaliplatin.
 - At least one anti-VEGF pathway inhibitor (bevacizumab and/or aflibercept and/or ramucirumab and/or regorafenib).
 - At least one anti-EGFR mAb (cetuximab or panitumumab).
 - Patients with known MSI-H/dMMR tumours are eligible if they have received previous treatment with immune checkpoint inhibitors according to approved indication.
- Participants must have progressed during or within 6 months of the last administration of the last standard chemotherapy regimen. Participants who have withdrawn from standard treatment due to unacceptable toxicity warranting discontinuation of treatment and precluding retreatment with the same agent prior to progression of disease will be eligible to enter the study.
- Participants who received adjuvant/neoadjuvant chemotherapy and had recurrence during or within 6 months of completion of the adjuvant/neoadjuvant chemotherapy are permitted to count the adjuvant/neoadjuvant therapy as one regimen of chemotherapy.

6a Participants should have received previous treatment with commercially available anti-EGFR mAbs for ≥ 16 weeks.

7. Ability to swallow oral medication.

8a. Estimated life expectancy ≥ 12 weeks. This criterion should be rechecked at inclusion visit (Safety Lead-in part) or randomisation visit.

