5.2.1.3.3. Previous therapies for colorectal cancer

The existence of a previous drug treatment (Yes, No) is defined from the presence, or not of an “anatomical therapeutic chemical classification” and/or a “preferred name” for the previous drug treatment at inclusion visit.

The existence of a previous metastatic drug treatment (Yes, No) is defined from the presence, or not of an “anatomical therapeutic chemical classification” and/or a “preferred name” for the previous drug treatment after the date of 1st metastasis.

The existence of a previous adjuvant drug treatment (Yes, No) is defined from the presence or not of a previous drug treatment with an adjuvant indication.

The existence of a previous neoadjuvant drug treatment (Yes, No) is defined from the presence or not of a previous drug treatment with a neoadjuvant indication.

The existence of a previous fluoropyrimidine drug treatment (Yes, No) is defined from the presence, or not of a previous drug treatment belonging to the list 3678.0.

The existence of a previous irinotecan drug treatment (Yes, No) is defined from the presence, or not of a previous drug treatment belonging to the list 3674.0.

The existence of a previous oxaliplatin drug treatment (Yes, No) is defined from the presence, or not of a previous drug treatment belonging to the list 3675.0.

The existence of a previous anti-VEGF monoclonal antibody drug treatment (Yes, No) is defined from the presence, or not of a previous drug treatment belonging to the list 4281.0.

The existence of a previous anti-EGFR monoclonal antibody drug treatment (Yes, No) is defined from the presence, or not of a previous drug treatment belonging to the list 4280.0.

Number of prior regimens for mCRC is calculated as the sum of previous drug treatments for mCRC except if reported in a maintenance indication.

The duration of previous metastatic regimen containing anti-EGFR monoclonal Anti Body (months) is defined as (last previous anti-EGFR monoclonal Anti Body drug treatment end date – first previous anti-EGFR monoclonal Anti Body drug treatment start date)/30.44.

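### SAP Table (5.2.1.3.2) 1 moves a missing end date of the last prior therapy to the earliest possible day, which overstates the treatment-free interval, in two cases by nearly the whole regimen

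*SAP*

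**What the plan says.** SAP 5.2.1.3.2, Table (5.2.1.3.2) 1, has three rows for the end date of the last prior therapy:

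- Wholly missing: "end date of the last prior therapy = start date of the last prior therapy + 1day".
- Only the year known: "start date of the last prior therapy + 1day if same year"; otherwise "end date of the last prior therapy = 01/01/yyyy".
- Only the day missing: start + 1 day if the month and year match the start; otherwise "end date of the last prior therapy = 01/mm/yyyy".

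The same table sets a wholly missing start date of a previous treatment to the inclusion date.

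Three baseline variables use these dates:

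- "Treatment free interval (months) is defined as (date of first IMP intake", less the end date of the last prior anti-cancer therapy, divided by 30.44. Drug treatment, radiotherapy and surgery all count as therapy.
- The progression-free interval subtracts the same end date from the date of progression. Patients who progressed during the last regimen are given one day.
- The anti-EGFR duration (SAP 5.2.1.3.3) is the "last previous anti-EGFR monoclonal Anti Body drug treatment end date" less the first anti-EGFR start date, divided by 30.44.

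The end-date rows name only the last prior therapy. For other therapies SAP 5.1.6 applies: "If no specific management of dates is defined, missing information is substituted as defined below". Table (5.1.6) 2 then gives the 1st of the month, 1 January, or no substitution if the date is wholly missing.

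SAP 3.2.4.2 summarises and lists both intervals. SAP 3.2.4.5 summarises the anti-EGFR duration but plans no listing of it.

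**The concern.** Every branch for the last prior therapy takes the earliest day that the known part of the date allows. With a known start date the error therefore runs one way: the therapy looks shorter than it was and the treatment-free interval looks longer. The only exception is a therapy that began and ended on the same day, where start + 1 day is one day late.

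These variables describe how refractory the treated patients were. A participant who came almost straight from months of chemotherapy can appear to have been off treatment for half a year or more.

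The rule also runs against the SAP's other stop dates, which are imputed late: last study-drug intake (Table (5.1.5) 1), concomitant and further anti-tumour treatments (Tables (5.2.1.5) 1 and 2) and adverse event recovery (Table (7.1) 3). No reason is given for the opposite choice here. The limits that the protocol supplies, 16 weeks of prior anti-EGFR therapy and a 4-week washout, are not used as bounds.

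**Working it through.** The documents state no figure that rests on this rule, so there is none to reproduce. The rules were applied to example dates. **The dates are assumptions.** The rules, formulas and the 30.44-day month come from SAP 5.1.3, 5.1.6, 5.2.1.3.2 and 5.2.1.3.3; the 16-week minimum comes from Protocol 5.1.2.

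**1. Treatment-free interval = (first dose − end of last therapy)/30.44**

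Example A: regimen 10 Jan to 28 Jun 2022, first dose 1 Aug 2022.

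| End date recorded | End date used | Interval |
|---|---|---|
| complete | 28 Jun 2022 | 34 d = 1.1 months |
| day missing | 1 Jun 2022 | 61 d = 2.0 months |
| year only, or wholly missing | 11 Jan 2022 | 202 d = 6.6 months |

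The last row adds 202 − 34 = 168 days, which is the 169-day regimen less one day.

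Example B: regimen 10 Oct 2021 to 10 Aug 2022, first dose 15 Sep 2022.

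| End date recorded | End date used | Interval |
|---|---|---|
| complete | 10 Aug 2022 | 36 d = 1.18 months |
| year only | 1 Jan 2022 | 257 d = 8.44 months |
| wholly missing | 11 Oct 2021 | 339 d = 11.14 months |

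The year-only row adds 257 − 36 = 221 days (7.26 months), the time from 1 January to the true end.

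**2. Upper limit for a missing day.** In a 31-day month the shift is at most 30 days: 30/30.44 = 0.99 months. If end days are uniform over a 30-day month, the mean shift is 14.5 days, about 0.5 month.

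**3. Effect on a group mean.** One participant like Example A among 25 moves the mean by 168/25 = 6.7 days, or 0.2 months. The median moves little.

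**4. Anti-EGFR duration.** If the last therapy is the only anti-EGFR course and its end date is wholly missing, the duration is 1/30.44 = 0.03 months. The entry minimum is 112/30.44 = 3.68 months.

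**5. Where negative durations come from.** The last-therapy rows were applied to start dates over two years and regimen lengths from 0 to 693 days, with known or partial starts. The shortest imputed duration was +1 day. Negative values come from other rules:

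- Table (5.1.6) 2, earlier anti-EGFR course starting 15 Mar 2021: an end recorded as 2021 becomes 1 Jan 2021, −73 d = −2.40 months; an end recorded as March 2021 becomes 1 Mar, −14 d = −0.46 months.
- Wholly missing start set to inclusion (15 Sep 2022), known end 10 Aug 2022: −36 d = −1.18 months.

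**6. Both dates missing.** The end becomes inclusion + 1 day. With the first dose 0 to 3 days after inclusion, the treatment-free interval is −1 to +2 days (−0.03 to +0.07 months), so here it is deflated.

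**The case against.** The best case for leaving the rule alone is that little depends on it. The randomised part is cancelled (SAP 1), subgroups are not applicable (SAP 2.3), and no test, safety endpoint or monitoring rule uses these variables. Sites must check the washout and the timing of progression at entry, and data are queried, so a wholly missing or year-only end date for the most recent therapy should be uncommon. Medians and quartiles are reported, and refractoriness is also described without dates, through the reason for stopping the last regimen. Start + 1 day suits surgery, which counts as a therapy. All of this stands and limits the weight of the point. It does not make the rule right for drug regimens that last months.

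A reader might infer more than the documents support:

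- **That the start + 1 day rule gives negative durations.** It does not when the start is known or partly known (working, step 5).
- **That the progression-free interval is inflated in the same way.** The SAP already gives one day to patients who progressed during the last regimen, and the reason for stopping is collected (SAP 3.2.4.5). In Example A, a 168-day (5.5-month) interval would appear only if that override were programmed from imputed dates, which the SAP does not say.
- **That eligible patients would appear to breach the 6-month entry criterion.** The criterion reads "Participants must have progressed during or within 6 months of the last administration of the last standard chemotherapy regimen". The SAP interval runs from any last therapy, including radiotherapy and surgery; the criterion section also admits patients who stopped for toxicity; and 5.5 months is inside the limit. No SAP section derives eligibility or deviations from these variables.
- **That anti-EGFR duration is generally corrupted.** The 0.03-month figure needs the last therapy to be the only anti-EGFR course, and SAP 5.2.1.3.3 does not itself cite the last-therapy rows. For an earlier course, a wholly missing end date is left unsubstituted.

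**Conclusion.** The rule as written gives a wrong treatment-free interval. With a known start date, and leaving aside one-day therapies, the overstatement is the regimen length less one day when the end date is wholly missing or year-only in the start year. It is the time since 1 January when the year is later than the start year, and at most about one month when only the day is missing. An anti-EGFR duration of 0.03 months is possible under the narrow conditions above. Negative durations are a separate fault, of Table (5.1.6) 2 and of the row that sets a missing start to inclusion.

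The consequence is confined to descriptive Safety Set baseline results. The sizes rest on assumed dates, and the documents do not say how many dates are partial. It is worth correcting because it is cheap and the listed values would mislead, but no trial conclusion depends on it.

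**What to change.** In SAP 5.2.1.3.2 and 5.2.1.3.3:

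1. Month missing or end date wholly missing: do not impute. Report the treatment-free interval and the anti-EGFR duration as not calculable, with the count.
2. Only the day missing: impute within the known month (mid-month, for example), bounded below by the start date and above by the inclusion date.
3. Apply items 1 and 2 to earlier courses in place of Table (5.1.6) 2.
4. Remove the substitution of the inclusion date for a wholly missing start when durations are calculated. Changing the end-date rows alone would leave those negative values in place.
5. State that the one-day progression-free interval rule uses the recorded reason for stopping the last regimen (SAP 3.2.4.5), not imputed dates.

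The cost is SAP wording and a few lines of derivation code. The downside is that a few participants become not calculable for these variables.

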5.2. Non-screening criteria

5.2.1. General criteria

11. Pregnancy, possibility of becoming pregnant during the study and breast-feeding women.

12. Unlikely to cooperate in the study.

13a. Participation in another interventional study at the same time or within 4 weeks prior to the inclusion visit (Safety Lead-in part) or randomisation visit. Participation in study follow-up part without IMP administration, non-interventional registry or epidemiological study is allowed.

14a. Patients currently receiving or having received anticancer therapies within 4 weeks prior to the inclusion visit (Safety Lead-in part) or randomisation visit.

15. Participant already enrolled in the study (informed consent signed).

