5.2.1.5. Concomitant treatments

The anatomical therapeutic chemical classification (ATC code = 5 digits) is composed of 4 levels:

- The first (1 digit) represents the anatomo-physiological class.
- The second (2 digits) represents the pharmacological class.
- The third (1 digit) represents the pharmacological sub-class.
- The last (1 digit) represents the therapeutic class.

The existence of a concomitant treatment (Yes, No) is defined from the presence, or not, of an Anatomical therapeutic chemical classification and/or Preferred name.

The periods considered for the analysis are:

At inclusion for which treatments:

- With start date \leq inclusion date and stop date \geq inclusion date or missing are taken into account. Inclusion date is equal to the date of inclusion visit, *i.e.* A000/D000 visit date.

Before the treatment period for which treatments:

- With start date $<$ first IMP intake date are taken into account.

During the treatment period for which treatments:

- With start date \geq first IMP intake date and $<$ (*), or
- With start date \leq first IMP intake date and stop date \geq first IMP intake date or missing

After the treatment period for which treatments:

- With start date \geq (*), or
- With start date \leq (*) and stop date $>$ (*) or missing.

(*)*max (first intake date of last cycle + 28 days of trifluridine/tipiracil, first intake date of last cycle + 28 days of futuximab/modotuximab)*

The following rules for substitution of missing or incomplete start and stop dates are so that the concomitance period is maximised:

CL3-95026-001 - Statistical Analysis Plan | VV-TMF-130355 | 1.0

Table (5.2.1.5) 1 - Substitution rules of concomitant treatments intake dates

Date to substitute		Substituted date
Start date	../mmm/yyyy	If the year and the month are the same as the year and the month of inclusion then Start date = Inclusion date , otherwise Start date = 01/mm/yyyy
/yyyy	If the year is the same as the year of inclusion then Start date = Inclusion date , otherwise Start date = 01/01/yyyy
/....	If stop date is non-missing and inferior to inclusion date then: Stop date Else: Inclusion date
Stop date	../mmm/yyyy	If patient died same month and year then Date of death Else Last day of the month/mmm/yyyy
/yyyy	If patient died same year then Date of death Else 31/DEC/yyyy
/....	If patient died then Date of death Else No substitution (i.e., treatment considered as still ongoing)

Note:/mm/yyyy = missing day

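### The SAP dates a previous cancer treatment with no recorded start to the inclusion date, without the end-date check used for concomitant treatments, so the anti-EGFR duration can come out negative or too short

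*SAP*

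**What the plan says.** SAP 5.2.1.3.2, Table (5.2.1.3.2) 1, gives substitution rules for the dates of the cancer history. Under "Missing start date of a previous treatment", when day, month and year are all absent, the substituted value is "Inclusion date". No condition refers to the end date. In the same table, a wholly missing end date of the last prior therapy becomes that therapy's start date plus one day.

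Other rules bear on this row:

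- Protocol 5.2.1, criterion 14a, bars entry to "Patients currently receiving or having received anticancer therapies within 4 weeks prior to the inclusion visit".
- SAP Table (5.2.1.5) 1, for concomitant treatments, has a guard: "If stop date is non-missing and inferior to inclusion date then" the stop date is used, and the inclusion date only otherwise.
- SAP Table (5.1.6) 2, the default where no specific rule exists, leaves a wholly missing date unsubstituted.
- SAP 5.2.1.3.3 defines the anti-EGFR regimen duration as the last anti-EGFR end date minus the first anti-EGFR start date, divided by 30.44. SAP 3.2.4.5 lists it for reporting.
- SAP 5.2.1.3.3 identifies metastatic drug treatment from the coded name "for the previous drug treatment after the date of 1st metastasis". Adjuvant use "is defined from the presence or not of a previous drug treatment with an adjuvant indication", and neoadjuvant use is defined in the same way.
- On the regimen count: "Number of prior regimens for mCRC is calculated as the sum of previous drug treatments for mCRC except if reported in a maintenance indication".

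**The concern.** A rule for an unknown start date should give a date that could be true, or none. This one gives a date that criterion 14a rules out for a prior anticancer drug in an eligible participant, and that lies after any end date the site did record. The row also stands apart from the SAP's general default and from its own rule for concomitant treatments.

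At stake is the description of who was treated. Prior anti-EGFR exposure defines this population (criterion 6a requires at least 16 weeks), and its duration is computed from the start date. With about 25 participants, one negative or shortened value shows in the minimum and can shift the mean. Start dates may also decide whether a drug counts as metastatic therapy.

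**Working it through.** The plan states no figure to reproduce. The check applies the rule to example cases.

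**Inputs from the documents.** Substituted start = inclusion date (SAP Table (5.2.1.3.2) 1). Washout of 4 weeks = 28 days (criterion 14a). Minimum anti-EGFR exposure of 16 weeks = 112 days (criterion 6a). Months = days/30.44 (SAP 5.1.3). About 25 participants (SAP 1.3).

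**Assumed for illustration.** Inclusion on 1 September 2022; first metastasis on 1 March 2020.

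**Case 1: one anti-EGFR course, start unknown, ended 28 days before inclusion (4 August 2022).**
- Substituted start: 1 September 2022.
- Duration = (4 August - 1 September)/30.44 = -28/30.44 = -0.92 months.
- Minimum consistent with entry = 112/30.44 = 3.68 months.
- An earlier end gives a larger negative value.
- The course was metastatic in any case, so its class does not change.

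**Case 2: two anti-EGFR courses, start of the earlier one unknown.**
- If the first start is the minimum of the available dates, the substituted inclusion date loses to the known start of the second course.
- Reported: end of course 2 minus start of course 2. True: end of course 2 minus start of course 1. The value is too short by the gap between the two starts.
- If only the later course lacks a start, the duration is unaffected.

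**Case 3: adjuvant drug, start unknown, ended 31 December 2018.**
- End minus substituted start = -1340 days; -1340/30.44 = -44.02 months. The SAP does not tabulate this as a duration, but the dates are out of order.
- If the start is compared with first metastasis, 1 September 2022 is after 1 March 2020, so the drug is classed as metastatic while remaining adjuvant by indication.
- If the end is compared, 31 December 2018 is before 1 March 2020 and the drug is not metastatic. The SAP does not say which date is compared.

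**Case 4: last prior therapy, both dates unknown, with the row applied to it.**
- Start = 1 September 2022; end = start + 1 day = 2 September 2022. The order is correct, but for a drug barred by criterion 14a neither date is possible.

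**The guarded rule of Table (5.2.1.5) 1 on the same cases.** Case 1: start = end, difference 0 instead of -28 days. Case 3: start = 31 December 2018, before first metastasis, so not metastatic on either reading. Case 4: unchanged. The guard restores the order of dates when the end is known, but a zero-length course is also wrong as a duration, and the guard does not help when both dates are missing.

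**Size of a Yes/No shift, where one occurs.** 1/25 = 4 percentage points.

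**The case against.** The strongest reply is that this is a small inconsistency with few certain consequences. Much of that stands.

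- **Metastatic class.** A reader might infer that every drug with an unknown start becomes metastatic therapy. The SAP does not support that. Only a drug given before first metastasis can be misclassified, and only if its start date is the one compared.
- **Regimen count.** A reader might infer that each such drug adds a prior mCRC regimen. The count is of treatments for mCRC, less those reported as maintenance, with no date rule. An extra regimen follows only if membership is taken from the date-based class.
- **Baseline rows.** A shift of 4 points per affected participant is not general. Criterion 5b requires at least two prior regimens for mCRC, so nearly everyone already has metastatic treatment. An agent-specific row moves only if that agent was given solely before metastasis and the start date is compared. Adjuvant and neoadjuvant rows rest on indication and do not move.
- **Impossibility.** The row covers treatments, not only drugs. Criterion 40a allows short-course palliative radiotherapy within 4 weeks of inclusion, and entry deviations can occur. The claim therefore holds for prior anticancer drugs in eligible participants.
- **Eligibility.** It is decided at screening and deviations are reported separately, so this rule does not affect who was eligible.
- **Likelihood.** A wholly missing start may be least likely for anti-EGFR therapy, whose duration sites had to establish for criterion 6a. That is plausible, but the documents give no counts.
- **Cost of not substituting.** Without a start date, the start-plus-one-day rule for the end date has no input, and an interval that depends on it is missing. That is preferable to an interval built on an invented date.

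None of this defends the row itself.

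**Conclusion.** The concern holds in a limited form. Followed as written, the row places the start of a prior anticancer drug after any known end date. It makes the anti-EGFR duration negative when the only course lacks a start (-0.92 months when it ended 28 days before inclusion), or too short when the earlier of two courses does. These results need only a wholly missing start, a known end date and, for the shortened value, a first start taken as the earliest available date.

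Reclassification of a (neo)adjuvant drug as metastatic is possible but depends on the start date being the one compared. An added mCRC regimen depends further on the count following that class. Neither should be stated as certain.

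The effect is confined to descriptive baseline tables in about 25 participants. The dose-limiting toxicity, adverse event and best overall response analyses do not use this date. The number of wholly missing start dates is unknown and probably small. This is a minor correction, worth making because it costs little.

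**What to change.** 1. In Table (5.2.1.3.2) 1, for a wholly missing start date of a previous treatment, make no substitution, in line with the default in Table (5.1.6) 2.
2. Leave the anti-EGFR duration missing when its start is unknown. State this explicitly for participants with several courses: a minimum taken over the known starts alone would still give the shortened value of case 2.
3. If a date is needed to order treatments, use the end date when it is known and before inclusion, as in Table (5.2.1.5) 1, but do not compute a duration from it.
4. Classify metastatic use and count mCRC regimens from the indication recorded in the e-CRF, as is already done for adjuvant and neoadjuvant use, not from a substituted date.
5. Do not cap the date at 4 weeks before inclusion; that would misdate palliative radiotherapy allowed by criterion 40a.

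The cost is one table row and short additions to the derivations in SAP 5.2.1.3.3, with no new data provided the e-CRF indication identifies metastatic use. If the tables already exist, list the wholly missing start dates first; if there are none, nothing needs rerunning.
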